6.2 Subject Characteristics

6.2.1 Subject Disposition

The subject disposition table will summarize the following and will be presented for all subjects by treatment group and overall:

- The number of subjects enrolled
- The number of subjects screen failed
- The number of subjects re-screened
- The number of subjects randomized
- The number and percentage of randomized subjects discontinued from the study
- The number and percentage of randomized subjects who completed the study
- The number and percentage of randomized subjects in the ITT population
- The number and percentage of randomized subjects in the PP population
- The number and percentage of randomized subjects in the Safety population

The number and percentage of randomized subjects who discontinue from the study and the primary reason for discontinuation will also be summarized by treatment group and overall.

The number and percentage of enrolled subjects meeting each inclusion/exclusion criteria will be summarized overall.

6.2.2 Protocol Deviations

A protocol deviation (PD) is defined as a divergence or departure from the requirements and procedures described in the study protocol and protocol amendments. The study PD Plan describes the procedures for reporting PDs from all sites into a global PD Log and reconciliation of this PD Log with the clinical database. All PDs in the global PD Log will be classified by the Medical Monitor into one of the categories shown in **Table 3** below.

Table 3: Classification of Protocol Deviations

1	Informed Consent Form Non-Compliance
2	Inclusion/Exclusion Non-Compliance
3	Investigational Product Non-Compliance
4	Prohibited Concomitant Treatment
5	Protocol Procedure Non-Compliance – Safety
6	Protocol Procedure Non-Compliance – Efficacy
7	Protocol Procedure Non-Compliance - Safety AND Efficacy
8	Protocol Procedure Performed Out of Visit Window
9	Randomization Procedure not Followed
10	Other

Appendix 3 of the PD Plan defines how each PD that may occur during the study should be classified.

The number and percentage of subjects with any PD and the number and percentage of subjects with each category of PD will be summarized by treatment group and overall for the ITT population.

Protocol Deviations from the global PD Log that may impact the co-primary efficacy analyses are those classified as “Inclusion/Exclusion Non-Compliance”, “Investigational Product Non-Compliance”, “Prohibited Concomitant Treatment”, “Protocol Procedure Non-Compliance – Efficacy”, “Protocol Procedure Non-Compliance – Safety AND Efficacy”, “Protocol Procedure Performed Out of Visit Window”, “Randomization Procedure not Followed” or “Other”. All PDs within these classifications will be reviewed by the Medical Monitor and the sponsor, and those deviations impacting the co-primary efficacy results will be identified in the global PD Log and reviewed by the study statistician. Subjects with such events will be excluded from the PP population.

The following criteria will be derived programmatically using the data from the clinical database and relevant external vendors. Subjects meeting any of these criteria will also be excluded from the PP population.

- Did not complete the study to Week 12.
- Vaginal dryness assessment not available at Baseline.
- Vaginal dryness assessment not available at Week 12.
- pH assessment not available at Baseline.
- pH assessment not available at Week 12.
- Proportion of superficial cells from vaginal smear not available at Baseline.
- Proportion of superficial cells from vaginal smear not available at Week 12.
- Proportion of parabasal cells from vaginal smear not available at Baseline.
- Proportion of parabasal cells from vaginal smear not available at Week 12.
- Received study treatment that was not the allocated treatment for that subject.

Subjects to be excluded from the PP population will be identified prior to database lock and before the treatment codes are unblinded. In the case of administration of incorrect medication kits, it will not be possible to identify whether any subject received study treatment other than their allocated treatment until unblinding is performed. Any subject known to have received incorrect kits will be reviewed post unblinding and excluded from the PP population if necessary.

The number and percentage of subjects meeting any criteria for exclusion from the PP population and the number and percentage of subjects meeting each criterion will be summarized by treatment group and overall for the ITT population.

6.2.3 Background and Demographic Characteristics

The following demographic characteristics will be summarized by treatment group and overall for the ITT population:

- Age (years) recorded directly on the eCRF
- Race (American Indian or Alaska Native; Asian; Native Hawaiian or Other Pacific Islander; White; Black or African American; Other)

Demographic data will be summarized using summary statistics for continuous variables (number of subjects [n], mean, standard deviation [SD], median, quartiles, minimum and maximum) or by way of group frequencies and percentages for categorical variables, as appropriate.

6.2.4 Treatment Exposure and Compliance

Study treatment exposure and compliance will be summarized by treatment group and overall for the Safety population.

Study Treatment Data

Subjects are instructed to bring their used and unused study treatment and unused applicators to the Week 3, Week 8 and Week 12 visits. All used applicators will be discarded by the subjects in their normal household waste. Compliance will be evaluated at the site, by reviewing the study treatment and the returned supplies. The following data related to administration of study treatment will be collected:

- [A] The date of first administration of study treatment will be captured on the 'Study Drug Administration – Baseline' page of the eCRF.
- [B] Ongoing study treatment data will be captured at the Week 3, Week 8 and Week 12 visits on the 'Study Drug Administration and Compliance – Cumulative' page of the eCRF. This log page includes, for each kit number: the date dispensed, the date returned, whether the tube of gel was returned, the number of applicators returned, the number of applicators used and the number of applicators lost/missed/damaged.
- [C] When the subject completes or discontinues from the study, the date of last administration of study treatment will be captured on the 'End of Study' page of the eCRF.

Exposure

Extent of exposure to study treatment is defined as:

$$\text{Extent of Exposure (days)} = \text{Date of Last Administration of Study Treatment}^{[C]} - \text{Date of First Administration of Study Treatment}^{[A]} + 1$$

The date of last administration of study treatment will be taken from the 'End of Study' page of the eCRF wherever available. If this is missing or not known, the date of last administration of study treatment will be assumed to be the latest date that a kit is returned on the 'Study Drug Administration and Compliance – Cumulative' page^[B] of the eCRF.

If no kits were dispensed according to the 'Study Drug Administration and Compliance – Cumulative' page^[B], but the study treatment was administered at Baseline according to the 'Study Drug Administration – Baseline' page^[A], the date of last administration of study treatment will be assumed to be equal to the date of first administration of study treatment, i.e. exposure will be calculated as equal to 1 day.

Extent of exposure (days) will be summarized using summary statistics for continuous variables (number of subjects [n], mean, standard deviation [SD], median, quartiles, minimum and maximum).

Compliance

The first administration of study treatment will be conducted at the Baseline visit, either by the investigator or by the subject in the presence of the investigator. Study treatment will then be administered once daily, at bedtime, until the Week 3 visit, and twice weekly after the Week 3

visit until the Week 12 visit. Therefore, the expected number of total applications for each subject will be calculated in 3 stages, as follows:

(1) The expected number of applications from Baseline to Week 3 will be calculated as:

$$\text{Expected Applications from Baseline to Week 3} = \text{Date of Week 3 visit} - \text{Date of Baseline visit}$$

This calculation assumes no application of study treatment on the day of the Week 3 visit, based on the bedtime dosing regimen.

If a subject discontinues prior to the Week 3 visit, the date of last administration of study treatment from the 'End of Study' page of the eCRF will be used instead, and the expected number of applications will be calculated as:

$$\text{Expected Applications from Baseline to Week 3} = \text{Date of Last Administration of Study Treatment}^{[C]} - \text{Date of Baseline Visit}$$

(2) The expected number of applications from Week 3 to Week 12 will be calculated using the algorithm below.

(i) The duration, in weeks, between the Week 3 visit and the Week 12 visit will be calculated as:

$$\text{Weeks from Week 3 to Week 12} = (\text{Date of Week 12 Visit} - \text{Date of Week 3 Visit}) / 7$$

(ii) If (i) is an integer, i.e. a number of whole weeks, the expected number of applications from Week 3 to Week 12 will be calculated as:

$$\text{Expected Applications from Week 3 to Week 12} = (\text{Weeks from Week 3 to Week 12}) \times 2$$

(iii) If (i) is not an integer and the decimal part of (i) is < 0.5 , the expected number of applications from Week 3 to Week 12 will be calculated as:

$$\text{Expected Applications from Week 3 to Week 12} = [(\text{Weeks from Week 3 to Week 12}) \times 2] + 1$$

(iv) If (i) is not an integer and the decimal part of (i) is ≥ 0.5 , the expected number of applications from Week 3 to Week 12 will be calculated as:

$$\text{Expected Applications from Week 3 to Week 12} = [(\text{Weeks from Week 3 to Week 12}) \times 2] + 2$$

(3) The expected number of total applications from Baseline to Week 12 will be calculated as:

$$\text{Expected Applications from Baseline to Week 12} = \text{Expected Applications from Baseline to Week 3} + \text{Expected Applications from Week 3 to Week 12}$$

The actual number of total applications for each subject will be calculated as the total of all applicators used from all kits according to the 'Study Drug Administration and Compliance – Cumulative' page^[B] of the eCRF.

The percentage compliance for each subject will then be calculated as:

$$\frac{\text{Actual Number of Total Applications}}{\text{Expected Applications from Baseline to Week 12}} \times 100$$

Treatment compliance (%) will be summarized using summary statistics for continuous variables (number of subjects [n], mean, standard deviation [SD], median, quartiles, minimum and maximum). The number and percentage of subjects with compliance by category (< 80%, 80% - 120%, >120%) will also be presented. The denominator of percentage will be the number of subjects who received study treatment and have a calculated compliance value available.

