3.1 Study Design

This study is a double-blind, randomized, dose-ranging, placebo-controlled multicenter study with four parallel groups. Approximately 25 sites in Europe will be included in the study. The study setting will include academic hospitals and gynecological clinics. The study population is postmenopausal women who report moderate to severe vaginal dryness as their most bothersome symptom in addition to other symptoms and/or signs of postmenopausal vulvovaginal atrophy.

After providing informed consent, potential subjects will be evaluated during the screening period to determine if they are eligible to participate in the study. A screening identification number will be assigned to each eligible subject according to their order of arrival into the study at screening visit. Subjects who meet all of the inclusion criteria (see Section 4.1.1) and none of the exclusion criteria (see Section 4.1.2) will be randomized into the study. A total of 280 subjects will be enrolled and randomly allocated to one of the four treatment groups (0.005%, 0.002%, or 0.0008% estriol vaginal gel or placebo vaginal gel); the allocation to treatment group will be 1:1:1:1. A blocked randomization across the entire study (i.e. all sites as a whole) will be used. Subjects will be assigned a randomization code according to their order of arrival into the study at the Baseline Visit. Initial treatment consists of daily vaginal administration of 1 gram of randomly-assigned estriol gel or placebo gel using the supplied applicator. After 21 days of daily administration, treatment will continue with twice-weekly administration up to Week 12 (i.e., Mondays and Thursdays).

The duration of trial participation for each woman is expected to be approximately 20 weeks (from Screening to End-of-Study phone call) although the time on study drug will be approximately 12 weeks. Subject completion is defined as the completion of all phases of the study, including the End-of-Study phone call to be performed for safety purposes at Week 16.

An overview of the study visit procedures is given in the Schedule of Events (Table 1). Details of specific procedures and testing are provided in Section 6.

Table 1: Schedule of Events

Procedure	Screening Visit	Baseline	Week 3	Week 8	Week 12/ Early Termination	Week 16/ End of Study Phone Call
Visit Window (days)	-30 to -1	1	21 ±3	56 ± 5	84 ± 5	112 ± 5
Informed consent	X					
Randomization		X				

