5.1 Method of Assigning Subjects to Treatment Groups

Subjects will be randomly assigned to receive 0.005% estriol vaginal gel, 0.002% estriol vaginal gel, 0.0008% estriol vaginal gel, or placebo vaginal gel using a 1:1:1:1 allocation ratio. Subjects will be assigned a randomization code according to their order of arrival into the study at the Baseline Visit.

The randomization schedule is prepared by the designated unblinded statistical programmer and reviewed and distributed by the designated unblinded statistician of

[REDACTED]

[REDACTED]
[REDACTED]
[REDACTED]
[REDACTED]
[REDACTED]
[REDACTED]

[REDACTED]
[REDACTED]
[REDACTED]
[REDACTED]

[REDACTED]
[REDACTED]
[REDACTED]
[REDACTED]

[REDACTED]
[REDACTED]
[REDACTED]
[REDACTED]
[REDACTED]
[REDACTED]

All subjects will start treatment with a single daily application of 1 g of gel during the first 3 weeks of study participation, and then twice weekly from Weeks 4 to 12. Study drug will be administered at bedtime, except the first dose, which will be administered by the investigator or by the subject in the presence of the investigator at the office at baseline visit. Twice weekly dosing during Weeks 4 through 12 is recommended to be preferably carried out on, for example, a Monday and Thursday schedule.

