5.4 Management of Clinical Supplies

5.4.1 Study Drug Packaging and Storage

Estriol vaginal gel and matching placebo will be prepared in aluminum tubes (with internal lacquer) closed with a polyethylene screw cap, containing 10 g of drug product, packaged and shipped by [REDACTED] to the designated packaging/labeling vendor ([REDACTED]). The designated packaging/labeling vendor ([REDACTED]) will then ship the experimental product to the study sites. The investigational product is packaged as a kit containing a tube of vaginal gel and ten 1-g capacity single-use vaginal applicators.

The studies of stability with the investigational product packaged in 10-g tube indicate that the product should be stored under conditions not to exceed +25°C.

Packaging and labelling of the medicinal products will be performed in accordance with GMP and national regulatory requirements.

Each study participant will be provided with an adequate number of 10-g tubes and 1-g capacity vaginal applicators to fulfill the dosing regimen requirements. Study drug provided to each subject at the Baseline Visit will consist of three kits, each containing one 10-g tube and 10 applicators (for 21 expected applications). At the Week 3 Visit, each subject will receive two kits of the study drug/applicators (for 10 expected applications), and at the Week 8 Visit, two additional kits of study drug/applicators (for 8 expected applications) will be provided.

The Principal investigator or sub-investigator must explain to the subject how to administer the vaginal gel. The first application should be performed at site at baseline visit by the investigator or by the subject in the presence of the investigator. Subjects will be instructed to administer the rest of the treatment applications at bedtime to allow for maximum retention of the gel.

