6.1.3 Week 3 Visit

This visit will be scheduled on the day after having completed 21 days of treatment. For organizational reasons, a deviation of 3 days before or after the scheduled date is allowed, with the investigator attempting to schedule the visit as close as possible to the estimated ideal date.

The following procedures will be performed:

- Evaluation of symptoms and signs of vaginal atrophy, including vaginal dryness.
- Determination of vaginal pH
- Vaginal smear for evaluation of vaginal cytology
- Recording of adverse events
- Recording of concomitant medications

- Reconciliation of returned medication
- Dispensing adequate medication supplies via IWRS through the Week 8 Visit (two medication kits)

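### SAP 6.2.4 miscounts expected applications for early stoppers and part-weeks, and ends daily dosing at the Week 3 visit where other text says 21 days; only the descriptive compliance table is affected

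*SAP*

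**What the plan says.** **Regimen.** Protocol 3.1 states: "After 21 days of daily administration, treatment will continue with twice-weekly administration up to Week 12". SAP 3 carries the same sentence. The dosing paragraph in Protocol section 5 has daily use "during the first 3 weeks of study participation, and then twice weekly from Weeks 4 to 12". Protocol 6.1.3 sets the visit from the dosing: "This visit will be scheduled on the day after having completed 21 days of treatment". It adds that "a deviation of 3 days before or after the scheduled date is allowed".

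**Compliance (SAP 6.2.4).** Here the daily phase is tied to the visit: "Study treatment will then be administered once daily, at bedtime, until the Week 3 visit, and twice weekly after the Week 3" visit. Expected applications are counted in stages:

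- Stage 1 is the Week 3 visit date minus the Baseline date. The SAP explains why the end day is left out: "This calculation assumes no application of study treatment on the day of the Week 3 visit, based on the bedtime dosing regimen".
- For a woman who discontinues before Week 3, stage 1 is the last administration date minus the Baseline date.
- Stage 2 takes weeks as (Week 12 date − Week 3 date)/7. It doubles that figure, then adds nothing if it is an integer, 1 if its decimal part is below 0.5, and 2 otherwise.

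The numerator is all applicators used from all kits. The percentage is summarised for the Safety population as a continuous variable and in three classes: below 80%, 80% to 120%, and above 120%.

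**Exposure (same section).** Days of exposure are last dose date minus first dose date plus 1. For a woman dosed at Baseline with no kits on the log, "i.e. exposure will be calculated as equal to 1 day".

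**The concern.** A count of daily doses between two dosing days needs a +1. The reason given for omitting it, that the end date is a non-dosing visit day, cannot hold when the end date is the date of a dose. Stage 2 rounds up for a part-week but also keeps the part-week, so it counts it twice. Stage 1 moves the end of daily dosing with the visit date, although the regimen text fixes it at 21 days.

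At stake is whether the compliance table describes adherence or visit timing. Women who dosed perfectly and stopped within days would be shown as overusers. Women near 80% could change class because of their visit dates.

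**Working it through.** **Inputs.** Baseline is Day 1 and carries a dose (SAP 6.2.4). The Week 3 visit is due the day after 21 days of treatment, so Day 22, with a window of Day 19 to 25 (Protocol 6.1.3). On the same convention Week 8 is Day 57 and Week 12 is Day 85. The expected counts in SAP 4.1.2 to 4.1.4 are 21, 10 and 8.

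**The plan's own count.** Stage 1 = 22 − 1 = 21. Stage 2 = 2 × (85 − 22)/7 = 2 × 9 = 18, which is 10 to Week 8 plus 8 to Week 12. The total is 39, an exact match.

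**1. Early stop.** Suppose the last dose is on Day d, every daily dose was taken, and the Baseline dose is among the applicators logged. The SAP states no stage 2 value for this woman; I take it as 0. Compliance is then d/(d − 1):

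- Day 2: 2/1 = 200%
- Day 3: 3/2 = 150%
- Day 4: 4/3 = 133.3%
- Day 5: 5/4 = 125%
- Day 6: 6/5 = 120%
- Day 15: 15/14 = 107.1%
- Day 1: 1/0, undefined

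Days 2 to 5 fall in the class above 120%. The error also hides missed doses: 3 of 4 doses with the last on Day 4 scores 3/3 = 100%, not 75%.

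**2. Part-weeks.** With Week 3 on Day 22 and Week 12 on Day 84, the interval is 62 days, or 8.857 weeks. As written, stage 2 = 17.71 + 2 = 19.71 and the total is 40.71. One day more (63 days) gives 18 and 39, so the shorter interval expects more doses. Doubling whole weeks only gives 16 + 2 = 18 and a total of 39. The overcount is twice the part-week, from 2/7 = 0.29 to 12/7 = 1.71. At 62 days, 39 applications score 39/40.71 = 95.8%.

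**3. Switch day.** Hold Week 12 on Day 85 and let a woman take 39 applications (21 daily, then 18). The whole-week columns repair step 2 only, which isolates the effect of the visit anchor.

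| Week 3 visit | Stage 1 | Stage 2 as written | Expected as written | 39 scores | Expected, whole weeks | 39 scores |
|---|---|---|---|---|---|---|
| Day 19 | 18 | 19.86 | 37.86 | 103.0% | 37 | 105.4% |
| Day 20 | 19 | 19.57 | 38.57 | 101.1% | 38 | 102.6% |
| Day 21 | 20 | 19.29 | 39.29 | 99.3% | 39 | 100% |
| Day 22 | 21 | 18 | 39 | 100% | 39 | 100% |
| Day 23 | 22 | 19.71 | 41.71 | 93.5% | 40 | 97.5% |
| Day 24 | 23 | 19.43 | 42.43 | 91.9% | 41 | 95.1% |
| Day 25 | 24 | 19.14 | 43.14 | 90.4% | 42 | 92.9% |

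At Day 23 the excess is 2.71, of which 1.71 comes from the part-week and 1 from the anchor. Classes can change near 80%. At Day 25, 34 applications are 34/39 = 87.2% of the regimen but are reported as 34/43.14 = 78.8%. At Day 20, 31 applications are 31/39 = 79.5% but are reported as 31/38.57 = 80.4%.

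If the 21 ± 3 in the schedule tables is read as study day, the window is Day 18 to 24. Day 18 then expects 17 + 21.14 = 38.14, and 39 applications score 102.2%.

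**The case against.** **The visit anchor may be what is meant.** SAP 4.1.2 to 4.1.4 count applications between visits, and kits are dispensed by visit. No text says what a woman does between Day 21 and a late visit. This stands: stage 1 is in conflict with the regimen text, but it is not proven wrong. A reader might infer that supply settles it, since the Baseline kits are described as "each containing one 10-g tube and 10 applicators (for 21 expected applications". It does not. Three kits hold 30 applicators, enough for daily use up to a Day 25 visit; 21 is only the nominal count.

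**The Baseline dose may not be in the kit log.** It is recorded on its own page. If it is left out of the numerator, the early-stop ratio is (d − 1)/(d − 1) = 100%. That only moves the error: the normal formula then expects 21 where 20 are logged, and a perfect completer scores 38/39 = 97.4%. The two formulas cannot both be right. The 21 applications expected from the Baseline kits imply that the dose is counted.

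**Whole weeks were surely intended.** Probably so, but step (i) defines weeks as the unrounded quotient, and the later steps double that named quantity.

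**The Day 1 woman is not misreported.** This stands. Percentages use only women with a calculated value, so she drops out of the table.

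**Conclusion.** Two rules in SAP 6.2.4 are wrong as written: the early-stop formula, which is one dose short, and the part-week rule, which overcounts by up to 1.71 applications. A third, the end of daily dosing, contradicts Protocol 3.1, the protocol dosing paragraph and SAP 3. Across the Week 3 window, with Week 12 on Day 85, the part-week and switch-day problems together move a fully adherent completer only within 90.4% to 103.0%, so she stays in the 80% to 120% class. The early-stop error is large only for women who stop within days.

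The early-stop percentages assume that the Baseline dose is logged among kit applicators and that stage 2 is 0. The table assumes that the 21-day regimen is what women follow.

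A reader might infer that the efficacy results or the Per Protocol population are affected. The documents do not support that. No efficacy model uses the percentage, and it is not among the programmed Per Protocol exclusions in SAP 6.2.2. Product non-compliance enters that population through review of the deviation log, which the SAP does not tie to this percentage. Severity is minor.

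**What to change.** In SAP 6.2.4:

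- **Early stop.** Use last dose date − Baseline date + 1, and set stage 2 to 0.
- **Steps (iii) and (iv).** Round weeks down to whole weeks, double, then add 1 or 2.
- **Switch rule.** Use one rule throughout. By default, set stage 1 to 21 and count stage 2 from Baseline date + 21; an early stop is then a last dose on or before Day 21. If sites in fact switch women at the visit, keep the visit-based stage 1, align SAP 3 and the protocol dosing text to it, and still make the first two changes.
- **Numerator.** Confirm that the Baseline dose is counted among kit applicators used. If it is not, add it, or the corrected denominators will be one too high.

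Checks on the default rule: Week 12 on Day 85 gives 21 + 18 = 39 for any Week 3 date; Week 12 on Day 84 also gives 39; a last dose on Day 1 gives 1, and on Day 15 gives 15. The total still runs from 38 to 41 for Week 12 on Day 80 to 90, as it should, because twice-weekly dosing continues to that visit.

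The cost is a few lines of SAP text and one derived variable, using dates already collected. Sites need do nothing beyond answering the two queries. The protocol wording changes only if the switch is confirmed to be at the visit.

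### SAP 6.2.4 leaves the last dose out of the expected applications for subjects who stop before Week 3, so their compliance is inflated, or undefined after one dose

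*SAP*

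**What the plan says.** SAP 6.2.4 defines compliance as applicators used, over all kits, divided by expected applications. The expected count has two parts, which are added to give "Expected Applications from Baseline to Week 12".

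- **Baseline to Week 3, subject reaches Week 3.** Expected = Week 3 visit date − Baseline date. The SAP gives the reason for not adding a day: "This calculation assumes no application of study treatment on the day of the Week 3 visit, based on the bedtime dosing regimen".
- **Baseline to Week 3, subject stops earlier.** The last administration date replaces the visit date ("the date of last administration of study treatment from the 'End of Study' page of the eCRF will be used instead") and the subtraction is otherwise unchanged.
- **Week 3 to Week 12.** The count is built on visit dates only: "The duration, in weeks, between the Week 3 visit and the Week 12 visit will be calculated as" the difference of the two visit dates divided by 7. Whole weeks are doubled. Otherwise the non-integer week count is doubled and 1 is added (decimal part below 0.5, rule iii) or 2 (0.5 or more, rule iv). There is no last-dose rule here, and no instruction to set this part to zero for a subject with no Week 3 visit.

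On dosing, "The first administration of study treatment will be conducted at the Baseline visit" and "Study treatment will then be administered once daily, at bedtime, until the Week 3 visit".

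The exposure formula in the same section is last administration date − first administration date + 1. For a subject dosed at Baseline with no kits logged, "exposure will be calculated as equal to 1 day".

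**The concern.** The visit-date subtraction is correct only because its end date carries no dose. The last administration date carries one by definition, so the stated justification fails exactly where the SAP makes the substitution. The numerator still counts every applicator, so numerator and denominator cover different days. The exposure formula handles the same pair of dates with + 1, so the section is inconsistent with itself.

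The error is largest for the earliest dropouts. It can place a fully compliant subject in the >120% category, lift a subject who missed doses out of the <80% category, and remove one-dose subjects from the table, because category percentages use only subjects with a calculable value.

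After Week 3 the basis changes. The end date is the Week 12 visit, which SAP 4.1.5 makes the Week 12/Early Termination visit for a dropout, so time between stopping drug and that visit is treated as time when doses were due.

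**Working it through.** **Inputs.** Formulas, rules (ii) to (iv) and compliance categories (<80%, 80%–120%, >120%): SAP 6.2.4. Week 3 visit on the day after 21 days of treatment, so Day 22 with Baseline as Day 1: SAP 4.1.3. Planned applications of 21, 10 and 8: protocol 5.4.1.

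**Reproducing the plan.** Completer with visits on Days 1, 22 and 85: 22 − 1 = 21; (85 − 22)/7 = 9 weeks, × 2 = 18 = 10 + 8; total 39. This matches protocol 5.4.1. The 21 covers Days 1 to 21, so the plan's own count includes the Baseline dose.

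**Stopping before Week 3, every daily dose taken.** First dose on Day 1, last on Day k. Expected = k − 1, used = k, compliance = k/(k − 1), taking the Week 3 to Week 12 part as 0.

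| Doses k | Expected (SAP) | Compliance (SAP) | With + 1 |
|---|---|---|---|
| 1 | 0 | undefined | 100% |
| 2 | 1 | 200% | 100% |
| 3 | 2 | 150% | 100% |
| 4 | 3 | 133% | 100% |
| 5 | 4 | 125% | 100% |
| 6 | 5 | 120% | 100% |
| 10 | 9 | 111% | 100% |
| 20 | 19 | 105% | 100% |

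With missed doses: last dose on Day 7 and 5 applicators used gives 5/6 = 83% under the SAP and 5/7 = 71% with + 1, a move from <80% into 80%–120%.

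Read literally, the second part has no Week 3 visit date for any of these subjects, so the total would be missing. The table assumes zero.

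**Stopping after Week 3.** Illustration: Week 3 visit on Day 22, sixth twice-weekly dose on Day 42, all doses taken, 21 + 6 = 27 used. The gaps from last dose to Early Termination visit are assumptions. Every interval below falls under rule (iv), so the second part is 2 × days/7 + 2.

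| Gap (days) | Interval from Day 22 (days) | Second part | Total expected | Compliance |
|---|---|---|---|---|
| 7 | 27 | 9.71 | 30.71 | 87.9% |
| 14 | 34 | 11.71 | 32.71 | 82.5% |
| 21 | 41 | 13.71 | 34.71 | 77.8% |
| 28 | 48 | 15.71 | 36.71 | 73.5% |

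Part of this shortfall is not due to the gap. Even with the visit on Day 42 itself (20 days), rule (iv) gives 2 × 20/7 + 2 = 7.71 expected for 6 taken: 27/28.71 = 94.0%. The cause is that rules (iii) and (iv) double the fractional week count and then add whole applications. Using whole weeks only, the four gaps give 8, 10, 12 and 14 expected, and 27/29, 27/31, 27/33 and 27/35 = 93.1%, 87.1%, 81.8% and 77.1%.

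**The case against.** The missing day before Week 3 has no good defence. One might say that the Baseline dose, applied at the site, is absent from the applicator log, so that the numerator is one short as well. But the completer count of 21 includes that dose, and so does the kit supply for 21 applications, so that reading would break the completer formula instead.

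The stronger objections concern what a reader might go on to infer.

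- **That the post-Week 3 count is simply wrong.** The SAP describes twice-weekly dosing until the Week 12 visit, and expected applications while still attending is a legitimate definition of adherence. What stands is that the SAP does not say it chose this, and uses last dose before Week 3.
- **That the post-Week 3 error has a known size.** The documents give no gap between last dose and Early Termination visit.
- **That a missing final visit makes the denominator the problem.** Applicator counts are taken at the Week 3, 8 and 12 visits, so without a final visit the numerator for that period is generally missing too.
- **That some 18% of subjects get wrong values and the comparison of arms is distorted.** The 18% is the sample-size allowance for all dropout, not a count of those affected. Inflation exceeds 120% only for fully compliant subjects stopping after two to five doses. The SAP plans descriptive statistics by arm and no test of compliance.

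**Conclusion.** The omitted last dose for dropouts before Week 3 is a definite error on the SAP's own text. It contradicts the + 1 in the exposure formula, and nothing elsewhere corrects it. Its size is k/(k − 1) for full compliance with daily dosing, taking the undefined Week 3 to Week 12 part as zero.

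The post-Week 3 rule is an inconsistency to be settled, not a proven error. The 87.9% to 73.5% range rests on an assumed dosing day and assumed gaps, and part of it comes from the fractional rules.

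The point is minor. It touches the descriptive Safety-population summary (Table 14.1.4). Compliance percentage is not among the programmed per-protocol exclusions in SAP 6.2.2. Deviations classed as investigational product non-compliance can lead to exclusion on review, but the documents do not say that this percentage feeds that review. No primary test, alpha or sample size changes.

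**What to change.** **Before Week 3 (needed).** Expected = last administration date − Baseline date + 1, with the Week 3 to Week 12 part set to 0. A fully compliant subject then scores 100% for any k, including k = 1. This is one line of SAP text and one of code.

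**After Week 3 (a choice to state).** Either say that counting to the Week 12/Early Termination visit is intended, or align it with the earlier rule. If aligned, end the interval at last administration date + 1 and use the whole-week part of the duration in rules (iii) and (iv). Ending at the last administration date alone would repeat the missing-day error: seven doses with the first on Day 22 and the last on Day 43 give 21/7 × 2 = 6 expected, 28/27 = 103.7%. Keeping the fractional count would leave the 94.0% case above.

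With both changes, a last dose on Day 42 gives 21 days, 6 expected and 27/27 = 100%; a last dose on Day 43 gives 22 days, 2 × 3 + 1 = 7 expected and 28/28 = 100%. One residue should be known. Under a strict Monday/Thursday schedule with a Friday Week 3 visit, a subject whose last dose is a Monday gets one expected application too many: last dose on Day 25 gives 4 days and 2 expected for 1 taken, 22/23 = 95.7%.

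The whole-week change also alters the expected count for completers whose interval is not a whole number of weeks: 62 days gives 18 instead of 19.71. It should therefore be made before unblinding and noted as a change. The cost is a few lines of text and code, with no change to data collection.
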